10.2.6 V5 (10 to 18 Months): device removal

The investigator will collect information regarding the surgical intervention for removal, including the intraoperative application time, and post-operative X-ray images. The investigator will collect information about changes in the concomitant medication, AEs and MDDs, if any, about the functional recovery of the treated limb (by the means of the ROM and the WBI when available).

Table 10.2: Events and Assessments Schedule

PERIODS		ENROLMENT		TREATMENT			
EVENT	Number	V0	V1	V2	V3	V4	V5
	Type	Screening	Surgery	Discharge	First control	Bone consolidation assessment	Device Removal
	Time*	N/A	Day 0	1 Week (± 2 days)	6 Weeks (± 2 weeks)	6-9 Months	10-18 Months
Inclusion / Exclusion Criteria	X						
Medical History	X						
Concomitant medication	X	X	X	X	X	X	
Demographics	X						
X-ray	X	X		X	X	X	
Clinical Examination	X			X	X	X	
Device application		X					
Range of motion	X		X	X	X	X	
Weight bearing index	X		X	X	X	X	
Safety Events		X	X	X	X	X	
MDDs		X	X	X	X	X	

Note: * timelines are estimated as average of the site normal clinical practice.

11. ADVERSE EVENTS AND SERIOUS ADVERSE EVENTS

11.1 Adverse Events

11.1.1 Definition of Adverse Event (AE)

Based on ISO 14155:2020, an “adverse event” is defined as untoward medical occurrence, unintended disease or injury, or untoward clinical signs (including abnormal laboratory findings) in subjects, users or other persons, whether or not related to the investigational medical device and whether anticipated or unanticipated.

This definition includes events related to the investigational medical device or the comparator.

This definition includes events related to the procedures involved.

For users or other persons, this definition is restricted to events related to the use of investigational medical devices or comparators.

Conditions or diseases diagnosed before subject inclusion in the study that are chronic but stable should not be recorded on AE pages of the CRF (they are a part of the Medical History). Chronic diseases which are diagnosed during subject participation in the study shall be recorded as AE/SAE.

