10.2 Description Event by Event

10.2.1 V0: Screening and Baseline

Prospective patients who meet the eligibility criteria will be enrolled in the study. Patients who agree to enter the study must sign the approved Informed Consent Form. Consented patients will have performed assessments as outlined in this protocol.

During the screening the investigator will evaluate the eligibility of the patients, checking all inclusion and exclusion criteria. Only those patients who meet all inclusion and exclusion criteria will be enrolled in the study. For each JPS implant a unique case number will be assigned (ID), and reported in the eCRF. Considering that each patient can contribute for more than one JPS implant: one patient can have more than one ID. In the eCRF the IDs are linked to the first ID assigned to the same patient by the clinical site. The patients not enrolled for non compliance will be considered as screening failures and will not be entered in the eCRF. Only for the enrolled patient, the Investigator will collect the demographic data and the medical history of the patient including information concerning the limb to be treated with JPS (baseline) such as the radiographic images and clinical examination.

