11.1.5 Procedures for Reporting and Recording AE, SAE and Medical Device Deficiencies

For the retrospective cohort the investigator will only collect AEs and MDDs already reported in medical file occurred since the application to the removal of the device.

For the prospective cohort, the investigator will follow the standard clinical practice to record data in the medical file, will follow the CA reporting procedure for any applicable case of AE and the manufacturer instruction to report any MDDs or AE as appropriate. Only after that, he will also record the AEs and MDDs in the eCRF.

For both cases the investigator, when reporting the event in the eCRF will assess:

- whether or not it is Serious and
- whether or not it is related to the use of the investigational device

, The investigator from surgery to device removal will record the AE on the Patient eCRF as appropriate. When applicable, the investigator should also provide any available information and diagnostic measurements (laboratory test, X-ray etc) related to the AE and store it in the eCRF.

In case of a serious adverse event related or possibly related to the investigational device, in addition to the recording of the adverse event in the eCRF, the investigator will send the compiled Safety Reporting Form (PO218-02 provided by the sponsor) to the following email addresses:

[contact]

Notification to Authorities by the sponsor

All SAEs related to an investigational procedure leading to death or imminent threat to death, a serious injury or disease, requiring a rapid corrective action must be notified by the sponsor to Competent Authority immediately or within 2 days at the latest.

In addition, as this is a PMCF observational study regarding a CE-marked device, the sponsor will comply with Articles 87 to 90 of MDR and detailed in MDCG 2023-3 (published in February 2023)

According to mentioned articles and guidelines, the sponsor will report to the competent authority all incidents that will occur during the use of the medical device covered by this study by specific reporting. For serious incidents with the most urgency, the reporting will be through Manufacturer Incident Report MIR 7.2.1 and sent to the competent authority with the most urgency and in any case no later than 10 days as well as to the local EC. For all other incidents, this timeline is within 30 days.

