13.2 Subject Information and Consent

The aim of the study is to collect clinical data based on medical records for patients treated with the JPS system in the past for whom follow-up assessment and JPS removal is already done (retrospective group) and for patients who has undergone JPS implantation and will have follow-up assessments and JPS removal (prospective group).

All subjects should give informed consent to participate in this study. Prior to being enrolled into the study, each patient (if he/she is adult at the time of the screening visit), or his/her parents/legal representative (if he/she is minor at the time of the screening visit), will be required to give his/her written and dated informed consent to participate the study and to collect and process their clinical data, and to anonymously store the data electronically. Also minors patients will be informed as far as possible by the investigators about the study and will be given an age dedicated informed form. Their willingness or refuse to participate to the study, if expressed, must be taken into consideration by the investigator.

Each patient/parents/legal representative will have the opportunity to discuss the informed consent with the Investigator prior to sign it. The Investigator or his/her designee will inform all patient/parents/legal representative regarding the purpose of the study and the clinical data that will be collected. The Investigator will deliberate that, considering this is an observational Study, there are no foreseeable risks resulting from study participation as well as potential benefits that may result from participating in the study.

Each patient/parents/legal representative will be informed by the Investigator that he/she is free to refuse to participate in the study and, if he/she choose to participate, that he/she may withdraw from the study at any time without providing reasons. In addition, the patient/parents/legal representative will be informed that, in some necessary cases, the Investigator may prematurely terminate their participation providing an appropriate reason.

The Investigator will provide the patient/parents/legal Representative with contact details in case they need further information after ICF signature.

Each patient/parents/legal representative will be informed that his/her medical records will be subjected to review by the Sponsor representatives, and may be subjected to review for the

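### The adverse event definition separates medical history from adverse events at study inclusion, not at surgery, so a lasting complication in a subject included after surgery could be left out of the primary endpoint

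*Protocol*

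**What the plan says.** **The rule.** Protocol section 11.1.1 says: "Conditions or diseases diagnosed before subject inclusion in the study that are chronic but stable should not be recorded on AE pages of the CRF". It assigns these conditions to medical history. The next sentence is the counterpart: "Chronic diseases which are diagnosed during subject participation in the study shall be recorded as AE/SAE".

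**When subjects are included.** Section 13.2 requires consent first ("Prior to being enrolled into the study, each patient" must give it in writing, in person or through a parent or legal representative). It describes the retrospective group as those with follow-up and removal already complete; the Synopsis and section 10.1 agree. For prospective subjects, the inclusion criteria in 8.1 require that JPS surgery has taken place, and 10.1 describes the cohort as already implanted.

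**How events are collected.** For the retrospective cohort, section 11.1.5 says "the investigator will only collect AEs and MDDs already reported in medical file occurred since the application to the removal of the device". It then adds, without limiting this to one cohort: "The investigator from surgery to device removal will record the AE on the Patient eCRF as appropriate". Section 10.2.1 treats medical history as a baseline item about a limb still to be treated. Section 10.2.2 starts event collection at surgery. Table 10.2 has medical history at V0 only and safety events from V1.

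**How events are counted.** The primary endpoint is the percentage of subjects with at least one adverse event certainly or possibly related to JPS, up to device removal. SAP sections 23.1 and 23.1.3 take both the event and its relatedness from adverse event records.

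**The concern.** A cut at inclusion is harmless when inclusion precedes treatment. Here, for the retrospective cohort, everything between surgery and removal lies before inclusion. A complication that arose after plating and has since become stable was diagnosed before inclusion and is chronic but stable, so it meets the literal wording for medical history. The same could happen to a prospective subject who consents after implantation.

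The events exposed in this way are the lasting ones. Section 11.1.2 lists permanent impairment, including chronic disease, among its criteria for a serious event, so the rule could reach events that the protocol would class as serious. The effect has one direction: misfiling can remove a subject from the numerator but cannot add one. The SAP describes no step that recovers events from medical history. A misfiled condition would appear only among the baseline descriptives of SAP section 16.3, for example under the free-text category.

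**Working it through.** **Step 1. Set the rules side by side for a retrospective subject.** Take a stable, lasting condition first diagnosed between surgery and removal.

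| Source | Anchor | Where the condition goes |
|---|---|---|
| Protocol 11.1.1, first sentence | Inclusion | Medical history |
| Protocol 11.1.1, second sentence | Participation (undefined) | AE only if participation covers the implant period |
| Protocol 11.1.5 | Application to removal | AE |
| Protocol 10.2.1, 10.2.2, Table 10.2 | Baseline, then surgery onward | AE |

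The first row conflicts with the third and fourth, and the documents give no order of precedence. Acute or resolved events are unaffected, because 11.1.1 concerns only chronic, stable conditions.

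**Step 2. Reproduce the plan's own figure.** Section 12.2 gives 30 subjects at an expected 3 %, with the exact 95 % upper limit under 15 %. The expected count is 30 × 0.03 = 0.9, about 1 event. The Clopper-Pearson upper limit is the (1 − α/2) quantile of Beta(x + 1, n − x) for a two-sided interval, or the (1 − α) quantile for a one-sided bound. For 1/30, the one-sided 95 % bound is 14.86 %, which reproduces the plan; the two-sided 95 % limit is 17.22 %. The steps below use two-sided limits, because section 12.3.2 asks for a lower and an upper limit, and add the one-sided reading.

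**Step 3. Sensitivity to one subject.** For x = 0 the two-sided limit reduces to 1 − (α/2)^(1/n). At n = 30 this is 1 − 0.025^(1/30) = 11.6 % at 95 %, and 1 − 0.024^(1/30) = 11.7 % at the SAP's 95.2 %.

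| Subjects with an event | Upper limit, 95 % | Upper limit, 95.2 % | At most 15 %? |
|---|---|---|---|
| 0/30 | 11.6 % | 11.7 % | yes |
| 1/30 | 17.2 % | 17.4 % | no |
| 1/40 | 13.2 % | 13.3 % | yes |
| 2/40 | 16.9 % | 17.0 % | no |

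The cap is 40 implant cases, so n = 40 assumes one implant per subject. With the one-sided 95 % bound the change comes one event later: at n = 30 between 1 event (14.9 %) and 2 (19.5 %); at n = 40 between 2 events (14.9 %) and 3 (18.3 %). On either reading a single subject can decide the result.

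**Step 4. Range of possible bias, by assumption only.** Let r be the share of subjects included after removal, and s the share of subjects with a related event whose only such event is chronic, stable and misfiled. Neither is in the documents. If the event rate is the same in both cohorts and misfiling occurs only among subjects included after removal:

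observed rate = true rate × (1 − r × s)

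Take a true rate of 10 %, inside the state-of-art range of 5.1 % to 15.0 %:

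- r = 0.25, s = 0.10: 10 % × (1 − 0.025) = 9.75 %
- r = 1, s = 0.5: 10 % × (1 − 0.5) = 5.0 %

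The chance of 0 events in 30 is 0.90^30 = 4.2 % with no misfiling, and rises to 4.6 % and 21.5 % in these two cases. If sites follow 11.1.5, s = 0 and there is no bias.

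**The case against.** The strongest reply is that 11.1.1 is the usual rule for pre-existing conditions, loosely worded, and that the rest of the protocol shows what was meant. Section 11.1.5 has a specific instruction for the retrospective cohort, medical history is a baseline item, and event collection starts at surgery. Most of the named conditions in SAP section 16.3 are underlying diseases, not complications. An investigator would have to disregard several sections to misfile an event. This stands as far as intent goes, and it makes correct recording a realistic outcome. It does not remove the conflict: 11.1.5 sets the collection window, while 11.1.1 says what is kept off the adverse event pages, and no text ranks them.

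Three stronger readings are tempting, and the documents do not support them.

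- **That lasting complications do drop out of the endpoint.** This assumes that the literal reading of 11.1.1 prevails. The documents show only that it could.
- **That the sentence on chronic disease diagnosed during participation can never cover retrospective subjects.** Participation is not defined. The Synopsis gives an 18-month observation period per subject and section 7.3 runs follow-up to removal. On that reading the sentence could cover the implant period.
- **That source data verification could not detect a misfiled event because the entry complies with 11.1.1.** The same entry would be at odds with 11.1.5. Section 14.2 plans 100 % verification of endpoint variables, so a monitor could query a charted complication that is missing from the adverse event form.

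It is also fair to say that the one-subject sensitivity applies to any missed event, whatever the cause. It shows how fragile the result is, not how large this particular bias would be.

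**Conclusion.** The concern holds as a moderate internal inconsistency. Section 11.1.1 is anchored to the wrong date for subjects included after surgery, and it conflicts with 11.1.5, 10.2.1, 10.2.2 and Table 10.2. It could cause under-recording in the primary endpoint, always in the direction of a safer-looking device.

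The expected size cannot be derived: the retrospective share, the timing of consent in the prospective cohort and the frequency of misfiling are not given. What can be said is conditional. If one subject's only related event were misfiled, the upper limit could pass from above 15 % to below it at the sample sizes planned. This takes the 15 % limit of sections 12.1 and 12.2 as the benchmark and two-sided exact intervals; on a one-sided reading the same happens one event later.

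**What to change.** **Protocol 11.1.1, both cohorts.** Replace the inclusion anchor with *before the JPS application surgery (V1)*, and the participation anchor with *between JPS application and device removal*. This brings 11.1.1 into line with 11.1.5 and changes no procedure, sample size or analysis.

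**Data already entered.** Before database lock, check medical history entries for onset after the surgery date. Record any that are found as adverse events, with seriousness and causality assessed. Timing matters: under SAP section 15, anomalies found in the results tables do not reopen the database, and reopening for the final analysis requires a rethink agreed with the sponsor.

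**Cost.** Two phrases in the protocol, handled under its amendment procedure, and a limited data check. The check may need the chart: SAP section 16.3 describes medical conditions as yes/no items and lists no onset date, and the CRF is not among the documents. The reported adverse event rate may become slightly less favourable.

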11.1.2 Definition of Serious Adverse Event (SAE)

In accordance with ISO 14155:2020, Serious Adverse Event (SAE) is an adverse event that led to any of the following:

- a) death,
- b) serious deterioration in the health of the subject, that either resulted in users, or other persons as defined by one or more of the following:
 - a life-threatening illness or injury, or
 - a permanent impairment of a body structure or a body function including chronic diseases, or
 - in-patient or prolonged hospitalization, or
 - medical or surgical intervention to prevent life-threatening illness or injury, or permanent
 - impairment to a body structure or a body function,
- c) led to fetal distress, fetal death or, a congenital abnormality, or birth defect including physical or mental impairment.

Planned hospitalization for a pre-existing condition, or a procedure required by the CIP without serious deterioration in health, is not considered a serious adverse event. If a subject is hospitalized to undergo a medical or surgical procedure as a result of an AE, the event responsible for the procedure, not the procedure itself, should be recorded as the event.

Hospitalizations for the following reasons will not be recorded as SAEs:

- Hospitalization or prolonged hospitalization for diagnostic or elective surgical procedures for preexisting conditions if not associated with the new occurrence of AE/SAE

- Hospitalization or prolonged hospitalization required to allow outcome measurement for the study if not associated with the new occurrence of AE/SAE
- Hospitalization or prolonged hospitalization for scheduled therapy of the target disease of the study if not associated with the new occurrence of AE/SAE.

11.1.3 Relationship between an AE/SAE and the use of the medical device

All AE/SAE will be judged by both the reporting Investigator and the sponsor as having a reasonable causal relationship to the investigational medical device. The relationship between the AE/SAE and the investigational medical device is considered

- **Certain** when the AE/SAE occurs in a plausible time relation to the application of the device and cannot be explained by a concurrent disease or other devices, drugs or chemicals. The response to withdrawal of the device (de-challenge) should be clinically plausible. The event must be definitive using a satisfactory re-challenge procedure if necessary;
- **Possible** when the AE/SAE occurs with a reasonable time relation to the application of the device, but it could also be explained by a concurrent disease or other devices, drugs or chemicals. Information on device withdrawal (de-challenge) may be lacking or unclear;

The AE/SAE is **Not Related** to the use of the investigational device in case of:

- existence of a clear alternative explanation, and/or
- unreasonable temporal relationship between application and/or
- non plausibility.

11.1.4 Medical Device Deficiency (MDD)

A “device deficiency” is defined as an “Inadequacy of a medical device related to its identity, quality, durability, reliability, usability, safety or performance, such as malfunction, misuse or use error and inadequate labeling.” A Medical Device Deficiency (MDD) is a device deficiency related to the device used for the clinical investigation (for the present study it is the JPS) and, when applicable, related to the comparative devices as well (for this CI it is not applicable because it is a not controlled study).

Device deficiencies include malfunctions, use errors, and inadequacy in the information supplied by the manufacturer including labeling, also related to the ancillary devices provided with the MD..

11.1.5 Procedures for Reporting and Recording AE, SAE and Medical Device Deficiencies

For the retrospective cohort the investigator will only collect AEs and MDDs already reported in medical file occurred since the application to the removal of the device.

For the prospective cohort, the investigator will follow the standard clinical practice to record data in the medical file, will follow the CA reporting procedure for any applicable case of AE and the manufacturer instruction to report any MDDs or AE as appropriate. Only after that, he will also record the AEs and MDDs in the eCRF.

For both cases the investigator, when reporting the event in the eCRF will assess:

- whether or not it is Serious and
- whether or not it is related to the use of the investigational device

, The investigator from surgery to device removal will record the AE on the Patient eCRF as appropriate. When applicable, the investigator should also provide any available information and diagnostic measurements (laboratory test, X-ray etc) related to the AE and store it in the eCRF.

In case of a serious adverse event related or possibly related to the investigational device, in addition to the recording of the adverse event in the eCRF, the investigator will send the compiled Safety Reporting Form (PO218-02 provided by the sponsor) to the following email addresses:

[contact]

Notification to Authorities by the sponsor

All SAEs related to an investigational procedure leading to death or imminent threat to death, a serious injury or disease, requiring a rapid corrective action must be notified by the sponsor to Competent Authority immediately or within 2 days at the latest.

In addition, as this is a PMCF observational study regarding a CE-marked device, the sponsor will comply with Articles 87 to 90 of MDR and detailed in MDCG 2023-3 (published in February 2023)

According to mentioned articles and guidelines, the sponsor will report to the competent authority all incidents that will occur during the use of the medical device covered by this study by specific reporting. For serious incidents with the most urgency, the reporting will be through Manufacturer Incident Report MIR 7.2.1 and sent to the competent authority with the most urgency and in any case no later than 10 days as well as to the local EC. For all other incidents, this timeline is within 30 days.

12. STATISTICS

12.1 Hypothesis

Hypothesis to test:

the observed primary safety endpoint for JPS ranges within the state-of-art (SOA) safety profile of equivalent plating systems.

State of art:

The proportion of subjects with serious/not serious adverse event surely or possibly related to the device reported in the scientific literature for the treatment of congenital deformities and fractures in lower limb of pediatric patients by the means of equivalent plating systems is between 5.1 % and 15.0 % depending on many factors, mainly the diversity of the primary diagnosis.

Assumption:

for the sole purpose of the sample size calculation, it was required to assume an expected proportion for the primary safety endpoint of JPS. The sample size, therefore, was calculated estimating the required number of subjects (considering the case the each patient contributes for only one JPS implant) so that the upper limit of the 95 % confidence interval for the expected proportion is ranged within the SOA (i.e. 95 % CI upper limit \leq 15 %).

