12.2 Sample size calculation

Assuming the expected proportion of patients with at least one serious/not serious adverse event surely or possibly related to JPS will be 3 %, 30 subjects (considering the case the each patient contributes for only one JPS implant) was calculated to be the sample size of this study so that the upper limit of the 95 % confidence interval for the primary endpoint, based on the exact binomial method, is under 15 %.

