23.1 ADVERSE EVENTS

The categorical variables to be described are, N and (%) and Clopper-Pearson confidence intervals will be shown at 95.2% as well:

- Implants with at least one adverse event
- Implants with at least one serious adverse event
- Patients with at least one adverse event
- Patients with at least one serious adverse event

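### The primary safety hypothesis and the sample size rest on different success criteria, and neither document says which one decides

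*Protocol*

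**What the plan says.** Protocol 12.1 and the statistical part of the synopsis give the hypothesis to test as "the observed primary safety endpoint for JPS ranges within the state-of-art (SOA) safety profile of equivalent plating systems". The next paragraph says that the literature rate for equivalent plates "is between 5.1 % and 15.0 % depending on many factors, mainly the diversity of the primary diagnosis".

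The Assumption paragraph of 12.1 brings in a second criterion. It opens "for the sole purpose of the sample size calculation, it was required to assume an expected proportion for the primary safety endpoint of JPS" and says that the number of subjects was chosen "so that the upper limit of the 95 % confidence interval for the expected proportion is ranged within the SOA", explained there as an upper limit of 15 % or less. Protocol 12.2 supplies the figures, "serious/not serious adverse event surely or possibly related to JPS will be 3 %, 30 subjects", with an upper limit that, "based on the exact binomial method, is under 15" %. The synopsis and SAP section 9 repeat the sizing text.

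Protocol 12.4 says only that descriptive statistics will be used to assess the hypothesis. SAP 14 sets the final confidence level at 95.2 %, and SAP 23.1 adds "Clopper-Pearson confidence intervals will be shown at 95.2% as well". The SAP states neither the hypothesis nor the 5.1 % to 15.0 % range. Its only 15 % figure is in the sample-size text of section 9. No success rule appears in SAP 14 or 23.1.

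**The concern.** The hypothesis, as worded, compares an observed proportion with a two-ended range. The sizing compares an upper confidence limit with a single ceiling. These are different statistics held against different bounds. The rate the design expects, 3 %, would itself fail the range in the hypothesis.

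At this sample size the choice determines the conclusion on the primary objective. The results are meant to support the benefit/risk ratio and retention of the CE mark, and the interim results feed the Clinical Evaluation Report. With no rule fixed, the conclusion could be chosen once the event count is known.

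**Working it through.** **Inputs.** State-of-the-art range 5.1 % to 15.0 % (Protocol 12.1, synopsis). Upper-limit criterion 15 %, exact binomial (12.1, 12.2). Assumed rate 3 %, N = 30 (12.2, SAP 9). Interval with lower and upper limits (12.3.2), at 95.2 % for the final analysis (12.5, SAP 14 and 23.1).

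**1. The plan's own N.** The expected count is 0.03 × 30 = 0.9, taken as 1 event. The exact upper limit is the p that solves P(X ≤ 1 | 30, p) = α.
- One-sided 95 % (α = 0.05): 14.86 %. With 29 subjects it is 15.34 %, so 30 is the smallest N that meets 15 %. The stated N reproduces.
- Two-sided 95 % (α = 0.025): 17.22 %. One event needs N = 35.
- Two-sided 95.2 % (α = 0.024): 17.35 %. One event needs N = 36.

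So N = 30 fits the stated criterion with 1 event only under a one-sided bound, while the documents describe a two-sided interval.

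**2. Which results pass at N = 30.** The range covers counts from 0.051 × 30 = 1.53 to 0.15 × 30 = 4.5, that is 2, 3 or 4 events. For 0 events the 95.2 % upper limit is 1 − 0.024^(1/30) = 11.69 %.

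| Events | Observed | 95.2 % two-sided upper limit | Observed in 5.1–15.0 % | Observed ≤ 15 % | Upper limit ≤ 15 % |
|---|---|---|---|---|---|
| 0 | 0 % | 11.69 % | fail | pass | pass |
| 1 | 3.33 % | 17.35 % | fail | pass | fail |
| 2 | 6.67 % | 22.22 % | pass | pass | fail |
| 3 | 10.0 % | 26.68 % | pass | pass | fail |
| 4 | 13.33 % | 30.88 % | pass | pass | fail |
| 5 | 16.67 % | 34.88 % | fail | fail | fail |

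The two-sided 95 % limits give the same passes and fails. A one-sided 95 % bound passes 0 or 1 event (9.50 %, 14.86 %).

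**3. Chance of a favourable conclusion at N = 30.**

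| True rate | Literal range, P(2 ≤ X ≤ 4) | Observed ≤ 15 %, P(X ≤ 4) | 95.2 % upper limit, P(X = 0) | One-sided 95 % bound, P(X ≤ 1) |
|---|---|---|---|---|
| 3 % | 22.5 % | 99.8 % | 0.97^30 = 40.1 % | 77.3 % |
| 15 % | 47.6 % | 52.4 % | 0.85^30 = 0.8 % | 4.8 % |
| 20 % | 24.5 % | 25.5 % | 0.1 % | 1.1 % |

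**4. What the upper-limit rule allows at larger N (95.2 %).** At N = 36, 1 event gives 14.64 % and passes. At a true 3 % the chance of passing is 0.97^36 + 36 × 0.03 × 0.97^35 = 0.334 + 0.372 = 71 %. At N = 40 still only 1 event is allowed, and the chance is 66 %. Two events are first allowed at N = 46.

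**The case against.** The strongest reply is that the authors plainly meant only the ceiling. The sizing sentence explains being within the state of the art as an upper limit of at most 15 %, with no lower bound, and nobody who assumes 3 % can regard a rate below 5.1 % as failure. The synopsis and 12.3.2 also present the primary endpoint with its confidence limits, so the observed endpoint need not mean a bare point estimate. Much of this stands.

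A reader might infer from the literal wording that at N = 30 the two rules have no passing result in common. That holds only if 5.1 % is a floor, and the documents argue against a floor. Without it, 0 events passes both rules. What remains is that 1 to 4 events pass on the observed rate and fail on the two-sided upper limit (2 to 4 events if the bound is one-sided). Taking the interval as part of the endpoint does not settle it either. If the whole interval had to lie inside the range, the lower limit would first exceed 5.1 % at 5 events (5.6 %), where the upper limit is 34.9 %, so nothing would pass.

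A reader might also infer that the point-estimate reading gives almost no protection against a poor device. That is too strong. About 50 % at the boundary is normal for a point-estimate rule, and the chance falls to 25.5 % at a true 20 %. The protection is weak, not absent.

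Finally, this is a descriptive, uncontrolled study, and the proportions and intervals will be reported whatever rule is used. But the protocol states a hypothesis to test and adds an O'Brien-Fleming adjustment to control type I error, which has no meaning without a decision rule.

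**Conclusion.** The concern holds in this form: the hypothesis and the sample size use different criteria, and no section says which decides. The size of the gap depends on the reading. With 5.1 % as a floor, 0 event is a pass on the upper limit and a fail on the hypothesis, and 2 to 4 events the reverse. Without the floor, the disagreement covers 1 to 4 events. Either way, 4/30 could be reported as within the state of the art with an upper limit of 30.9 %, and at a true 15 % the chance of a favourable conclusion moves between about 50 % and 0.8 %.

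These figures assume 30 evaluable patients, independent outcomes between patients, exact binomial limits, and the two-sided 95.2 % level unless a one-sided bound is named. The documents do not support the claim that the two rules can never agree, because they do not establish 5.1 % as a floor.

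**What to change.** In Protocol 12.1 and the synopsis, replace the hypothesis with one rule. JPS is within the state of the art if the upper limit of the two-sided 95.2 % Clopper-Pearson interval, for the proportion of patients with at least one certainly or possibly related adverse event, is 15.0 % or less. State that 5.1 % is not a lower bound for success. Copy the rule into SAP 14 and 23.1.

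State with it:
- At N = 30 the rule passes only with 0 events, which has a 40 % chance at a true 3 %. The expected result, 1/30, fails at 17.35 %.
- One event is allowed only from 36 evaluable patients, with a 71 % chance of passing at a true 3 %. The maximum of 40 implant cases less 10 % dropout is 36, but that gives 36 patients only if each contributes one implant.
- N = 30 matches the stated criterion with 1 event only under a one-sided 95 % bound (14.86 %).
- The rule was fixed after the interim analysis, which SAP 14 describes as already performed and used for the Clinical Evaluation Report.

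The edit is wording only and needs no new data. Its real cost is a claim harder to meet than on the point-estimate reading. That is why the confidence level, sidedness and number of evaluable patients should be settled together with the rule.
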